11.4 Ordinal Scale of Clinical Improvement, AUC Analysis

The computation of Area Under the Curve (AUC) provides a method to combine multiple timepoints of Ordinal Scale of Clinical Improvement within a specific time interval, into a single index. AUCs will be calculated using SAS macros incorporating the “trapezoidal rule” to compute the area of each individual small trapezoid whereby the total sum of those individual areas equals the total area under the curve (i.e., total AUC) for that time period.

In order to examine clinical improvement trends over the entire visit period from time points $t=$ Day 1 to $t=$ Day 90, the total AUC will be calculated by summing each individual trapezoid (Day 1 to Day 2, Day 2 to Day 3, Day 3 to Day 7, Day 7 to Day 15, Day 15 to Day 30, Day 30 to Day 60, and Day 60 to Day 90) for each treatment group. The resulting AUCs will be summarized descriptively using N, mean, standard deviation, median, range.

The AUCs of clinical improvement will be analyzed using a MMRM as described above (see Section 11.2).

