3.2 Study Endpoints

- All-cause mortality.
- Ordinal Scale of Clinical Improvement, absolute values and changes from start of treatment to Days 2, 3, 7, 15, and 30.
- Time to a 1-point decrease on the Ordinal Scale of Clinical Improvement from start of treatment.

- Area under the severity versus time curve, where severity is defined by the Ordinal Scale of Clinical Improvement and time is measured from start of treatment to Days 2, 3, 7, 15, and 30.
- Days of supplemental oxygen or mechanical ventilation from start of treatment (up to 90 days).
- First Intensive Care Unit (ICU) discharge
- Days in ICU from start of treatment (up to 90 days).
- Discharge from hospital.
- Days hospitalized from start of treatment (up to 90 days).
- Severity of ARDS as defined by the Berlin criteria, absolute values and changes from start of treatment to Days 2, 3, 7, 15, and 30.
- Cytokine and biomarker results, absolute values and changes from start of treatment to Days 2, 3, 7, 15, and 30.
- Adverse events (AEs) and serious adverse events (SAEs) within 90 days from start of treatment.

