9.4 Missing Data and Dropouts

The issue of how to handle missing data caused by dropouts in clinical studies is a research topic that is still under development in the statistical literature. As has been noted in the ICH-E9 guideline, “no universally applicable method of handling missing values can be recommended”. The best approach is to minimize the chance of dropouts at the design stage of the clinical study and during study monitoring.

In general, data will be analyzed as received from the clinical database. Hence, missing values will not be replaced by imputed values except for the following situations:

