9.4.3 Other Situations

For subjects who are withdrawn from the study prior to study completion, all data compiled up to the point of discontinuation will be used for analysis. All withdrawals will be included in all analyses up to the time of withdrawal.

Extra measurements (such as unscheduled or repeat assessments) will not be included in summary tables but will be included in subject listings. They will be used in summary tables which are not “time specific”, for example, summaries of maximum post dose values.

The original data will always be presented in the listings.

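### The Day 1–90 severity AUC is an unscaled sum: a living subject who leaves early gets a falsely low (better) value, missed visits have no rule, and an MMRM on one AUC per subject cannot correct this

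*SAP*

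**What the plan says.** - **Construction (SAP 11.4).** The AUC condenses the ordinal scores "into a single index". Over Day 1 to Day 90, "the total AUC will be calculated by summing each individual trapezoid", and the seven intervals are listed, ending with "Day 15 to Day 30, Day 30 to Day 60, and Day 60 to Day 90". The section has no rule for an interval with a missing end, and no division by observed time.
- **Model (SAP 11.4).** "The AUCs of clinical improvement will be analyzed using a MMRM as described above", with a pointer to SAP 11.2. That section fits the visit scores with baseline score and risk score as covariates and gives LS means by visit. It switches to a non-parametric version if a pre-test of variance or normality gives 0.10 or less. It also says that higher scores are worse.
- **Missing data (SAP 9.4).** Outside listed exceptions, "missing values will not be replaced by imputed values". The imputation rules that follow (9.4.1 and 9.4.2) concern adverse-event and medication dates, not ordinal scores.
- **Withdrawals (SAP 9.4.3).** "All withdrawals will be included in all analyses up to the time of withdrawal".
- **Endpoint list (SAP 3.2).** For the AUC, "time is measured from start of treatment to Days 2, 3, 7, 15, and 30". No Day 60 or Day 90 horizon appears.
- **Follow-up (Protocol 7.2 and 7.3).** Sites try to obtain the Day 90 assessments when a subject leaves early. Loss to follow-up means that the Day 90 contact failed. The SAP does not say where an early-termination score enters the AUC.

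**The concern.** An AUC in score-days grows with time observed as well as with illness. Scores run from 0 to 8, so every further interval adds area or leaves it unchanged. Taken together, the three SAP rules give a subject with short follow-up a low total, and that total enters the analysis as a complete, favourable observation.

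If one arm loses more living subjects than the other, part of the estimated AUC difference is a difference in follow-up. The AUC is a listed efficacy endpoint, and the SAP weighs the totality of evidence across endpoints, so a spurious difference would count towards proof of concept.

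**Working it through.** The plan states no AUC, SD, withdrawal rate or power, so there is no figure to reproduce. Visit days, scale and rules come from the SAP. Score paths, withdrawal rates and the two-sided 0.05 level are assumptions.

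**1. Interval widths.** Visits at Days 1, 2, 3, 7, 15, 30, 60 and 90 give widths 1, 1, 4, 8, 15, 30 and 30, total 89 days. The last two hold 60/89 = 67%. Each trapezoid is width × (left score + right score)/2.

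**2. Complete series, recovering subject.** Scores 5, 5, 5, 4, 2, 1, 1, 1 give 5 + 5 + 18 + 24 + 22.5 + 30 + 30 = 134.5.

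**3. Withdrawal.** A subject at score 5 throughout, last seen at Day 15, has 14 × 5 = 70. Had the subject stayed at 5 to Day 90, the AUC would be 89 × 5 = 445. A sicker path (5, 5, 6, then 6 to the end) has 532.5 if complete and 5 + 5.5 + 24 + 48 = 82.5 if last seen at Day 15. Both truncated totals rank ahead of the recovering subject's 134.5.

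**4. Early-termination score.** Suppose the Day 15 leaver's exit score of 5 is filed as Day 90. Under the listed intervals the total stays at 70, because Days 30 and 60 are missing. If the gap is bridged, it becomes 70 + 75 × 5 = 445. The SAP does not choose.

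**5. Missed interior visit.** Take the subject in step 2 without Day 60. Dropping both adjoining trapezoids gives 134.5 − 60 = 74.5. Bridging Day 30 to Day 90 gives 74.5 + 60 × 1 = 134.5, the complete value. For 5, 5, 5, 4, 3, 2, 1, 1 (complete: 168.5), the same gap gives 93.5 if dropped and 183.5 if bridged. The direction depends on the programming choice.

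**6. What the MMRM can do.** With one AUC per subject there is no within-subject correlation to borrow, and the model is an ANCOVA on baseline covariates. A truncated AUC is not flagged as missing, so a missing-at-random argument never applies to it.

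**7. Size under no drug effect**, 30 per arm, truncated sums. Negative values favour the arm that loses more subjects.

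| Withdrawal, arm v arm | Mean AUC difference | Rejection |
|---|---|---|
| 15% v 5%, last visit Day 15 | about −10 | 9–11% |
| 15% v 5%, separate simulation | about −9 | 8% |
| 10% v 0%, last visit Day 15, 30 or 60 | −9.2 | 7.0% |
| 20% v 10%, same | −8.9 | 5.8% |
| 20% v 0%, same | −18.4 | 13.1% |
| 30% v 10%, same | −17.9 | 13.1% |
| 10% v 10%, same | +0.7 | 5.0% |

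The last five rows used 1,500 replicates, withdrawal unrelated to score, and a complete-data mean of 182.8 (SD 93.9). The Monte Carlo error of a 5% rejection rate is √(0.05 × 0.95/1500) = 0.6 percentage points, so 5.8% is not clearly above 5%. The error of a mean difference is about 93.9 × √(2/30)/√1500 = 0.6, so −9 is clearly not zero and +0.7 is compatible with zero. A difference of 9.2 is 9.2/93.9 = 0.10 SD.

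**8. Alternative estimator.** Collecting terms, each score's weight is half the sum of its adjoining widths: 0.5 for Day 1, then 1, 2.5, 6, 11.5, 22.5, 30 and 15. Check on step 2: 2.5 + 5 + 12.5 + 24 + 23 + 22.5 + 30 + 15 = 134.5. With baseline as covariate, the Day 1 term drops out of the treatment difference. In the first scenario of step 7, this contrast from a visit-score MMRM had bias +0.6 and rejection 4% (500 replicates).

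**The case against.** **The SAP never says to sum only the available trapezoids.** It lists all seven as the total, and an incomplete AUC could be set to missing. In a simulation with withdrawal unrelated to outcome, that removed the bias (rejection about 4.5%). It is hard to square with SAP 9.4.3, which keeps withdrawals in all analyses, and it discards the scores they gave. What stands is that truncation comes from reading three sections together, not from one sentence.

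**A reader might infer that any missed visit lowers the AUC.** The documents do not support that. Nothing in SAP 11.4 says to drop both neighbouring trapezoids, and step 5 shows that bridging leaves the AUC unchanged or raises it. The fault there is an unstated rule.

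**The MMRM may have repeated records.** If the AUCs to Days 2, 3, 7, 15 and 30 in SAP 3.2 are the outcomes, a Day 15 leaver simply lacks the Day 30 value, which an MMRM can handle under missing at random. This is fair for that list. It does not rescue the single Day 1–90 total that SAP 11.4 defines, and the two sections need reconciling.

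**Follow-up is designed to limit loss.** Discharged subjects are followed by telephone, the ordinal scale is not restricted to inpatients, and Day 90 assessments are attempted at exit. This should reduce the number affected, but it supplies no rule for those who remain.

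**The stakes are limited.** The study is an exploratory pilot with descriptive p-values, and SAP 11.2 tests the same scores by visit without truncation. That bears on priority; the AUC estimate would still be distorted.

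**Conclusion.** The point holds for living subjects who withdraw or are lost before Day 90: the stated rules give them a truncated AUC that looks better. The direction is certain for a truncated sum of non-negative scores. For missed interior visits the method is undefined. The planned MMRM on one AUC per subject corrects neither.

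The size is conditional. With about 10 percentage points more withdrawal in one arm and no drug effect, the false difference is about 9–10 points and false positives about 7–11%, with one run at 5.8%. These figures rest on assumed paths and rates; the documents give none.

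Two stronger conclusions are not supported. A reader might infer bias whenever subjects withdraw, but equal withdrawal gave none under the null. A reader might also infer a large loss of power. One simulation with recovery twice as fast fell from 61% to 33%, but its scenario of 10% withdrawn and 10% missing Day 60 per arm scored the missed visit by deletion. Another path model with doubled recovery fell only from 98% to 93%, near its ceiling. The loss of power depends on the assumptions.

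The scoring of deaths is a separate matter. This should be changed, but it does not undermine the trial as a whole.

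**What to change.** In SAP 11.4:

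1. Estimate the treatment difference in AUC from the parametric SAP 11.2 MMRM of visit scores, as the weighted sum of visit LS-mean differences. The weights are 1, 2.5, 6, 11.5, 22.5, 30 and 15 for Days 2, 3, 7, 15, 30, 60 and 90.
2. Use matching weights for the SAP 3.2 horizons, where the last visit takes half its preceding width: 0.5 (to Day 2); 1, 0.5 (Day 3); 1, 2.5, 2 (Day 7); 1, 2.5, 6, 4 (Day 15); 1, 2.5, 6, 11.5, 7.5 (Day 30). Reconcile the Day 90 horizon of SAP 11.4 with that list.
3. Report this contrast with robust or bootstrap standard errors even if the SAP 11.2 pre-test selects the non-parametric MMRM, which may not give differences on the score scale.
4. For descriptive per-subject AUCs, bridge a missed interior visit between the adjacent observed scores, do not file an early-termination score as Day 90, and report subjects without the final visit separately rather than as complete.

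The cost is SAP wording, one weighted contrast from a model already planned, and a little more programming. No new data are needed. The downside is reliance on missing at random, which the SAP 11.2 MMRM already assumes.

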11.5 Time on Supplemental Oxygen or Mechanical Ventilation

The total time (days) on respiratory/ventilator (mechanical) support will be taken from the Respiratory/Ventilator eCRF page (dataset: QS1). The time will be calculated from the date/time that the subject required respiratory/ventilator support (eCRF checked “Yes” for this question) to the date/time that the subject did not need respiratory/ventilator support (eCRF checked “No” for this question). If a subject had multiple occurrences of needing mechanical support, then these times will be summed together.

Time on mechanical ventilation will be defined in two ways:

- (1) The interval from the subject’s date/time of the original mechanical ventilation collected (could be prior to study drug administration) to the date/time the subject is off mechanical ventilation. If a subject had multiple occurrences of needing mechanical support, then these times will be summed together.
- (2) The interval from the subject’s date/time of mechanical ventilation after study drug administration to the date/time the subject is off mechanical ventilation. If a subject had multiple occurrences of needing mechanical support, then these times will be summed together.

The censoring/imputation rules as defined above will be followed.

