## 1.2 Schema

### 1.3 Schedule of Activities

PROCEDURE / EVENT	SCREENING  Visit	TREATMENT PHASE 	FOLLOW-UP PHASE 								EVENT DRIVEN 
			Day 2	Day 3	Day 7 (± 1 day)	Day 15 (± 1 day)	Day 30 (± 3 days)	Day 60 (± 3 days)	Day 90 (± 7 days)		
Day	–5 to –1	Day 1 (IP Administration)									
Informed Consent	X										
Eligibility Assessment	X	X 									
Demographics	X										
Medical History	X										
Physical Examination	X	X 			X 	X 					
Vital Signs	X	X 	X	X	X 	X 	X 	X 	X 		
Respiratory / Ventilator Status 	X	X 	X	X	X 	X 	X 	X 	X 		
12-Lead ECG	X	X 			X 	X 	X 	X 	X 		
Pregnancy Test 	X										
Clinical Laboratory Testing 	X	X 	X	X	X 	X 	X 				
Blood Sampling for Proteomics 	X	X 	X	X	X 	X 	X 				
SARS-CoV-2 Testing	X										
Chest X-Ray	X				X 						
Ordinal Scale for Clinical Improvement	X	X 	X	X	X	X	X	X	X		
Randomization 	X										
Order Investigational Product 	X										

PROCEDURE / EVENT	SCREENING 	TREATMENT PHASE 	FOLLOW-UP PHASE 								EVENT DRIVEN 
			Visit	Day 2	Day 3	Day 7 (± 1 day)	Day 15 (± 1 day)	Day 30 (± 3 days)	Day 60 (± 3 days)	Day 90 (± 7 days)	
Day	-5 to -1	Day 1 (IP Administration)									
Administration of Investigational Product 		X									
Peripheral Venous Access Site Monitoring 		X									
Concomitant Therapies	X	X	X	X	X	X	X	X	X	X	
Adverse Events 	X	X	X	X	X	X	X	X	X	X	
Collection of Outcome Data 		X	X	X	X	X	X	X	X	X	

 Clinical laboratory conducted as part of standard of care within 7 days prior to protocol consent during index hospitalization may be used for screening visit assessments and eligibility determination.

 Eligible subjects will receive 1 dose of IP.

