 Follow-up phase will be conducted on Days 2, 3, 7 (± 1 day), 15 (± 1 day), 30 (± 3 days), 60 (± 3 days) and 90 (± 7 days). Follow-up will either be conducted in the inpatient setting or as a phone follow-up should the subject be discharged. Note that as long as the subject remains hospitalized on study the safety of the subject will be monitored on a daily basis per standard of care.

 Data that will collected on a subject-by-subject basis based on occurrence during study participation.

 Prior to baseline assessments on Day 1, Investigator is required to confirm the subject's eligibility based on the inclusion and exclusion criteria in [Section 5.1](#) and [Section 5.2](#).

 Assessment to occur prior to infusion on Day 1.

 Assessment will be conducted in the inpatient setting only if the subject is still hospitalized for this visit.

 Every 15 minutes from pre-infusion through 2 hours post-infusion.

 To capture type of ventilator and respiratory support (e.g., endotracheal ventilator, nasal O2 cannula, face mask, or ECMO) and twice daily SpO2 (%), FiO2 (%) and respiration rate (bpm).

 On treatment day, include immediately pre- and post-infusion.

 Only to be conducted for women of childbearing potential.

 Includes the following clinical laboratory samples: CBC, CMP, CRP, cytokine assay (IL-1, IL-6, TNF- $\alpha$ , INF- $\gamma$ , IL-10), troponin I, myoglobin, ferritin, and procalcitonin.

 Blood samples will be taken and submitted to a central laboratory for future proteomic assay assessment. Information on the assay and procedures for collection and shipping are located in the laboratory manual.

 Subjects will be randomized approximately 1 to 5 days prior to the planned infusion in Treatment Phase to allow enough time for IP ordering and delivery.

-  IP will be ordered approximately 1 to 5 days prior to the infusion (Day 1) in Treatment Phase to allow for enough time for IP delivery. Please see the IP Manual for ordering instructions and timelines.
-  Subjects will be observed for at least 2 hours post-infusion, including vital signs assessments every 15 minutes. The clinical site will observe local institutional policies related to parenteral infusions and post-infusion monitoring. A site Investigator will assess the subject for AEs.

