## **3 OBJECTIVES AND ENDPOINTS**

The primary objectives of the study are to determine the safety and effectiveness of intravenously infused CAP-1002 in improving clinical outcomes in severely or critically ill patients with COVID-19.

Several exploratory safety and efficacy endpoints will be measured to evaluate the effects of CAP-1002 treatment on the morbidity and mortality of severely or critically ill patients with COVID-19. The endpoints are as follows:

- All-cause mortality.
- Ordinal Scale of Clinical Improvement, absolute values, and changes from start of treatment to Days 2, 3, 7, 15, and 30.
- Time to a 1-point decrease on the Ordinal Scale of Clinical Improvement from start of treatment.
- Area under the severity versus time curve, where severity is defined by the Ordinal Scale of Clinical Improvement and time is measured from start of treatment to Days 2, 3, 7, 15, and 30.
- Days of supplemental oxygen or mechanical ventilation from start of treatment (up to 90 days).
- First Intensive Care Unit (ICU) discharge
- Days in ICU from start of treatment (up to 90 days).
- Discharge from hospital.
- Days hospitalized from start of treatment (up to 90 days).

- Severity of ARDS as defined by the Berlin criteria, absolute values, and changes from start of treatment to Days 2, 3, 7, 15, and 30.
- Cytokine and biomarker results, absolute values, and changes from start of treatment to Days 2, 3, 7, 15, and 30.
- Adverse events (AEs) and serious adverse events (SAEs) within 90 days from start of treatment.

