### **8.1.2 Respiratory and Ventilator Status**

Information pertaining to the respiratory and ventilator support during hospitalization will be collected including type of support.

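### The oxygen-days endpoint runs from start of treatment to Day 90, but SAP 11.5 neither starts total support at infusion nor says how it ends for a subject discharged on oxygen

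*SAP*

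**What the plan says.** The endpoint in Protocol Section 3, repeated in SAP 3.2, is "Days of supplemental oxygen or mechanical ventilation from start of treatment (up to 90 days").

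SAP 11.5 derives it. Total time on respiratory or ventilator support "will be taken from the Respiratory/Ventilator eCRF page (dataset: QS1"). On the start of the interval it says: "The time will be calculated from the date/time that the subject required respiratory/ventilator support", identified by a Yes on that page. The interval ends at a No on the same page, and repeated episodes are summed. Mechanical ventilation alone then gets two definitions: (1) from the original start, which "could be prior to study drug administration", and (2) from ventilation after study drug administration. For censoring and imputation, 11.5 refers to rules defined above.

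The Protocol 1.3 row "Respiratory / Ventilator Status" is marked at Screening, on Day 1 before infusion, and on Days 2 and 3. At Days 7, 15, 30, 60 and 90 it carries footnote 7: "Assessment will be conducted in the inpatient setting only if the subject is still hospitalized for this visit". Protocol 8.1.2 sets the same limit: "Information pertaining to the respiratory and ventilator support during hospitalization will be collected including type of support". Footnote 3 of the schedule says: "Follow-up will either be conducted in the inpatient setting or as a phone follow-up should the subject be discharged".

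**The concern.** The endpoint as declared is a count over a fixed window that opens at infusion and closes at Day 90. The derivation uses a different window. It can open before dosing, and for anyone who leaves hospital still on oxygen it has no defined close. A programmer following 11.5 literally would not obtain the declared quantity, and two programmers could reasonably obtain different ones.

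Pre-dose days cannot be affected by treatment. Under randomization they should fall equally on both arms, so they mainly dilute the comparison. The open end matters more, because the handling of discharge on oxygen decides what is measured. Closing the interval at discharge makes the endpoint partly a second measure of hospital stay, which is already a separate endpoint. Censoring at discharge makes the censoring depend on clinical recovery. Imputing to the end of study makes home oxygen look like the worst outcome.

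**Working it through.** The documents give no expected value, standard deviation or power for this endpoint, so there is no planned figure to reproduce. The check sets the passages side by side and then shows what the missing rule is worth.

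**Start of the interval.**
- Declared: start of treatment (Protocol 3, SAP 3.2).
- Derived: when support was required. SAP 11.6 and 11.8 both cite the first IP administration date; 11.5 does not.
- The assessment is made at Screening and before infusion, and SAP Section 2 puts screening about 1 to 5 days before dosing. Entry requires low oxygen saturation or COVID-19 cardiomyopathy (Protocol 5.1), and oxygen use is not excluded, so pre-dose oxygen is likely.
- Ventilation definition (2) supplies a post-dose start, but for ventilation only. Total support has no such version.
- Example: a subject discharged on Day 7 with oxygen stopped that day has 7 − 1 = 6 days as declared. With 1 to 5 pre-dose days included, the count is 7 to 11.

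**End of the interval.**
- Declared: up to 90 days. SAP 11.5 states no cap.
- Derived: a No on the Respiratory/Ventilator page. After discharge no such assessment is scheduled. That leaves 90 − 7 = 83 days uncovered for discharge on Day 7, 75 for Day 15 and 60 for Day 30.
- The rules cited as above: the only censoring rule before 11.5 is the survival rule in 11.1. The duration rules stand later, in 11.7. They cover no ICU admission, ICU stay through all of follow-up, death, withdrawal and database lock. None covers leaving hospital with support continuing.
- Other records: the ordinal scale is scored at every visit but has no level for oxygen at home. The Concomitant Therapies Log (Protocol 8.2.7) runs to study completion and may hold home oxygen, but 11.5 does not use it.

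**One assumed subject**, discharged on Day 7, with home oxygen to Day 30 and no pre-dose days. The declared count is 30 − 1 = 29 days.
- Closed at discharge: 7 − 1 = 6 days, an error of −23.
- Censored at discharge: 6 days without an event. No duration is observed.
- Imputed to Day 90: 90 − 1 = 89 days, an error of +60.

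**Two assumed arms**, each truly needing 25 days from infusion. A share of 40% goes home on oxygen, after 8 days (active) or 14 days (placebo).
- Closed at discharge: 0.6 × 25 + 0.4 × 8 = 18.2 and 0.6 × 25 + 0.4 × 14 = 20.6. The difference is 0.4 × (14 − 8) = 2.4 days, or 0.2 × 6 = 1.2 days if the share is 20%.
- Imputed to the 90-day maximum: 0.6 × 25 + 0.4 × 90 = 51 in both arms. The difference is 0, with each mean 51 − 25 = 26 days too high.

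Under closure at discharge, the spurious difference is the home-oxygen share times the gap in discharge day. For shares of 10% to 50% and gaps of 2 to 5 days, it runs from 0.1 × 2 = 0.2 to 0.5 × 5 = 2.5 days.

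**The case against.** A reader might infer that home oxygen is simply lost, so that the arm discharged earlier gains a false benefit of about 2.4 days. The documents do not support that. Section 11.5 sends unresolved intervals to censoring or imputation and nowhere closes them at discharge. SAP Section 11 makes a Cox model the default analysis, and that model would not credit a censored subject with stopping oxygen. The example's inputs are all assumed. In a blinded randomized trial, discharge timing has no evident reason to differ between arms unless treatment affects it. All of this stands, and it removes any claim about direction or size.

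A reader might also take "could be prior to study drug administration" as a decision to count pre-dose oxygen. It is not: those words belong to ventilation definition (1), definition (2) corrects for them, and intubated patients are excluded. For oxygen, the early start follows only from the missing anchor. It can be read as an omission, since SAP 3.2 states the right window.

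The case report form was not supplied. The link between dataset QS1 and the scheduled assessment rests on the matching name, and the page could be a running log. However, Protocol 8.1.2 separately limits collection to the hospital stay.

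Finally, this is one of 12 endpoints in a pilot study with descriptive p-values. That limits the weight of the point but does not reconcile 11.5 with the endpoint.

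**Conclusion.** The concern holds as a mismatch between the declared endpoint and its derivation, and it should be corrected. At the start, total support lacks an infusion anchor and may take in about 1 to 5 pre-dose days, mainly as noise. At the end, discharge on oxygen has no scheduled closing entry and no applicable rule. Depending on the rule adopted, oxygen days may be under-counted, informatively censored or over-counted, so no direction of bias can be stated. The 2.4-day difference illustrates one rule, closure at discharge, under assumed inputs; imputation to 90 days on the same inputs gives no difference between arms. The conclusion assumes that QS1 follows the scheduled respiratory assessment and that some subjects go home on oxygen. The documents do not give that share.

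**What to change.** In SAP 11.5:
- Start total support at the first IP administration date and cap it at Day 90. Keep pre-dose support as a baseline descriptor only; nothing is lost, because Protocol 8.2.6 already records earlier oxygen requirements as medical history.
- Replace the reference to rules above with explicit rules for an interval still open at discharge, death or withdrawal, separately for the time-to-event analysis and any continuous analysis.
- Obtain oxygen status and stop date after discharge from the existing phone visits. If those are complete, use the Concomitant Therapies Log and name it as a source.
- If neither source can supply the data, redefine and report the endpoint as in-hospital respiratory-support days from infusion.

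The cost is SAP wording plus, if calls remain, one item with a date on visits already scheduled. The documents do not say whether calls remain. The downside is that stop dates will rest on recall or on how completely the log was kept. The rules should be fixed before unblinding.
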